1. BACKGROUND AND RATIONALE

1.1. Study Synopsis

The ultimate goal of this proposed study is to evaluate potential clinical efficacy of a novel magnetic resonance imaging (MRI) approach, MR fingerprinting, capable of providing quantitative measures of important tissue properties, which could provide important insights into normal breast tissue. We will recruit a totally of 30 patients scheduled for screening breast MRI for high risk normal patients. The novel sequence, namely MR fingerprinting, will be added prior to the injection of MR contrast, followed by the rest of the clinical imaging sequences. Quantitative maps, including T1, T2map will be computed from MR fingerprinting.

1.2. Disease Background

In clinical setting, breast DCE MRI was performed for breast cancer staging, high risk screening, and problem solving when mammography, ultrasound and clinical findings were questionable. The protocol for screening MRI and clinical breast DCE MRI were the same. Patients were put on prone position with bilateral breasts fit in the dedicated breast coil. The following sequences will be taken: whole breast axial T1 weighted 3D SPGR, axial T2 weighted FSE with fat saturation, followed with axial 3D T1-weighted fat-saturated DCE MRI with one pre-contrast and three post contrast enhanced phases at the temporal resolution of 100 seconds followed with a high spatial resolution interview scan (0.9 mm isotropic 3D T1-weighted fat-saturated scan). DCE MRI has high sensitivity for breast cancer detection (95%) while lack of specificity (37-86%) between tumor types as overlap between findings of benign and malignant lesions and among different breast cancer subtypes [1]. Specifically, DCE MRI is also a powerful tool for neoangiogenesis evaluation or treatment response monitoring for breast cancer [2], with physio- pathologic measurements of the volume transfer constant (K^{trans}), fraction of extracellular extravascular space (v_e), and vascular density (v_p) [3]. To obtain these pharmacokinetic parameters, a relation between the signal enhancement and contrast agent concentrations is required. The native T1 (T_{10}) is calculated and then used to convert the signal enhancement curve to concentration curve [3]. The most commonly used method to measure T1 is variable flip angle (VFA) imaging which uses several short-repetition-time radiofrequency spoiled gradient-echo acquisitions with varying FAs [4-7]. However, the T1 measurement using VFA has been notified to be marked deviated up to 50% by the nonuniformity of the transmit radiofrequency (B_1) field even in 1.5 T [8]. It would be very important to obtain the most accurate T_{10} value of breast tumor before contrast medium injection to calculate the most accurate pharmacokinetic parameters across different platform, vendors and machines. Nevertheless, it is a daunting task to obtain quantitative measures of T_{10} independent of these potential confounding factors. The current paradigm of MRI is to use a set of scanner settings to generate an image ‘weighted’ a specific MR contrast mechanism (physical

parameter), where it is hoped that variations in the parameters will be accentuated. However, without quantitative knowledge of the parameters, the final image contrast may depend on many factors, which may complicate image interpretation and diagnostic performance [9]. Quantitative measurement can provide a great deal of information about tissue properties and pathological conditions, since these parameters ultimately determine the contrast that is observed in conventional images [10]. The investigational imaging sequence, MR fingerprinting, could be performed in a much shorter scanning time and provide more accurate quantitative tissue characteristics (T1 and T2 value).

Despite the irreplaceable roles of breast DCE MRI in clinical practice (most sensitive and accurate in breast cancer detection and staging, and even provide more insight on the perfusion and functional change in treatment response monitoring before the tumor size change in patient undergoing chemotherapy or target therapy), MRI has been pushed to its limit today. One of the principle limitations is that lack of quantitative information for tissue/structure characterization.

MR fingerprinting could be performed in a short time to obtain more accurate quantitative tissue characteristics (T1 and T2 value) simultaneously which would largely decrease examination time (which means reduce patient scanning time in the MR scanner, that is decreased patient suffering time on examination table and decrease examination expanse of hospital).

1.3. Conventional Imaging Modality

The clinical DCE MRI of breast have been widely used for breast cancer screening, detection, staging and treatment response monitoring for decades. This image modality outperforms mammography and ultrasound of breast in breast cancer detection and extent evaluation [11]. There is no radiation risk for this imaging examination. The only two drawbacks of this study are longer examination time and gadolinium based contrast medium usage. The patients need to be rested on the examination table in a fixed prone position (not very comfortable) with bilateral breasts been fitted in the breast coiled for at least 30 to 40 minutes.

As part of the MRI procedure subjects may receive a contrast agent called gadolinium. Gadolinium makes it easier to see details on the MRI pictures. An extremely rare disease called Nephrogenic Systemic Fibrosis (NSF) is associated with the use of gadolinium contrast agents in patients with chronic severe renal insufficiency or renal dysfunction due to hepato-renal syndrome or in the peri-operative liver transplantation period. Exclusion criteria for this study are in compliance with the Food and Drug Administration's advisory statements. If subjects have any problems with their kidneys, they may be at risk for a condition called Nephrogenic Systemic Fibrosis (NSF) or Nephrogenic Fibrosing Dermopathy. NSF has been reported to occur between 2 days and 18 months following injection of gadolinium. There is no known treatment for NSF. Some people have even died from this. Signs and symptoms of NSF may include: burning, swelling, hardening or tightening of the skin, blood vessels and internal organs (heart, lungs, liver; yellow spots on the white part of the eyes; joint swelling and stiffness; pain in the hip bones or ribs; muscle weakness.

Subjects' study doctor will check how well their kidneys work before they are given gadolinium. Depending on how well their kidneys work, they may be given a reduced dose or they may not be able to take gadolinium at all. NSF has not been reported in people with normal kidneys.

1.4. Investigational Imaging Modality

The purpose of this study is to evaluate the novel quantitative MRI techniques, namely MR Fingerprinting (MRF), in clinical studies to determine whether they can provide better, faster, and more useful tissue information for clinical diagnosis. The MRF does NOT require gadolinium contrast medium injection, and will be acquired in about 6 minutes scanning time before the clinical contrast enhancement examinations and 6 minutes at the end of study. This work has been published in Nature for its accurate quantification of proton density, T1, T2 relaxation times in the rapid multi-parametric MR technique[12]. Pilot studies with scans from hundreds of patients have demonstrated that the novel method can provide valuable information for various diseases in brain, liver, and prostate [13-16]. While it has shown great promise in these previous studies, clinical evaluation of this technique has been limited to a few medical centers worldwide due to complexity in installation, implementation and post-processing of the technique. [name], a newly recruited faculty at Department of Radiology, is a key developer of the MR Fingerprinting technique[16]. In this study, we propose to apply this novel technique at UNC and evaluate its performance for different conditions of breasts. We hypothesis that the quantitative MR imaging technique will lead to improved tissue characterization, diagnosis and quantification.

1.5. Rationale

This is a feasibility study of the use of the additional MRF scanning sequence with a total of 12 minutes scanning time to our clinical screening breast DCE MRI examination before contrast medium injection and at the end of scan. This additional scanning sequence may provide faster and better quantitative tissue characterization comparing to conventional MR sequences. There is no investigational contrast agent in this study. We propose that the additional MRF sequence may provide faster and more accurate tissue characteristics imaging for clinical evaluation of breast tissue. Patients will be enrolled in with scheduled high risk screening DCE MRI (n=30). The MR imaging will be performed in the clinical 1.5T MR scanners in UNC as normally done for the patients MRI schedule. We only add an additional MRF sequence within the MRI exam just prior to the contrast enhancement scan.

Quantitative measurement of the breast tissue will be performed after the MR exam. The ROI of normal breast parenchyma was recorded. The ROI will be saved and encoded to the T1 map, T2 map in MRF, T1 weighted imaging, T2 weighted imaging. A large variety of imaging ROI-based quantitative measures will be calculated among normal glands in bilateral breasts to evaluate different ROI characteristics among different patients and between bilateral breasts in each patient.

2. STUDY OBJECTIVES

2.1. Primary Objectives

The purpose of this study is to evaluate the novel quantitative MRI techniques, namely MR Fingerprinting (MRF), in clinical studies to establish the T1 and T2 value baselines of normal glandular tissue.

2.2. Primary Endpoint

The normal breast tissue T1, T2 value will be used to compare between sides in same patient and among the different patients and between two MRF sequences in pre-contrast phase and post contrast enhancement phase and also the differences between pre and post contrast enhancement phases.

3. PATIENT ELIGIBILITY

3.1. Inclusion Criteria

[figure not shown]
- 3.1.1.** English-speaking patients
- 3.1.2.** Ages 18 to 99 years old
- 3.1.3.** Scheduled to undergo a screening breast MRI study
- 3.1.4.** Capable and willing to provide signed informed consent

3.2. Exclusion Criteria

- 3.2.1. Claustrophobia**
- 3.2.2.** Presence of pacemaker, intracranial aneurysm clip, bladder stimulator, cochlear implant or metal near eyes or near pelvis that would create excessive imaging artifact
- 3.2.3.** Known hypersensitivity to [contrast agent] or to any component of [contrast agent] refractory to standard medications (antihistamines, steroids)
- 3.2.4.** Impaired kidney function (serum creatinine level > 1.8 mg/dl or a glomerular filtration rate < 60 as approximated using serum creatinine levels) unless anuric and on dialysis.
- 3.2.5.** Inability to **tolerate MRI (e.g., inability to lie flat for >1 hour)**
- 3.2.6.** Pregnancy or lactating female
- 3.2.7** Previous history of mastectomy.

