4.2.1. Enrollment/Recruitment

A total of 30 women will be enrolled to this study. The 30 study subjects will be consecutively recruited from women who are scheduled to undergo a screening MRI. Eligible patients will be identified by research staff review in coordination with the UNC Breast Clinic.

Once a patient has been referred, the patient will be approached by a coordinator from Radiology to assess interest in participation.

All eligible women who agree to participate in the study will be asked to come to their MRI appointment thirty minutes early to complete the informed consent process.

Review of the consent will take place in the privacy of an exam room, or when possible, a sample consent form will be sent to the patient via email prior to the patient's visit to allow for ample review.

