4.2.4. Medical Record Abstraction

The breast MRI report will be extracted one week after completion of the MRI exam for confirmation of normal status.

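### Mastectomy is the only past breast treatment excluded, so a breast with earlier conserving surgery or radiotherapy can enter the normal-gland baseline and the left-right comparison

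*Combined protocol and SAP*

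**What the plan says.** The primary objective (Section 2.1) is "to establish the T1 and T2 value baselines of normal glandular tissue". The primary endpoint (Section 2.2) uses the T1 and T2 values to "compare between sides in same patient and among the different patients", among other contrasts.

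Entry is broad. The only criterion describing the clinical setting is "Scheduled to undergo a screening breast MRI study" (Section 3.1), and women are "consecutively recruited from women who are scheduled to undergo a screening MRI" (Section 4.2.1). Section 3.2 has seven exclusions, of which "Previous history of mastectomy" is the only one about past breast treatment. Conserving surgery, radiotherapy and earlier breast cancer appear in neither list.

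Three places point towards normal tissue:
- The synopsis (Section 1.1) describes patients "scheduled for screening breast MRI for high risk normal patients".
- Section 1.5 says of the region of interest: "The ROI of normal breast parenchyma was recorded".
- Section 4.2.4 says: "The breast MRI report will be extracted one week after completion of the MRI exam for confirmation of normal status".

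Section 7.2 also calls the participants normal subjects. Section 7.3 contains no exclusion, adjustment or sensitivity analysis for a treated breast.

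**The concern.** A baseline for normal gland needs a definition of normal, and here treatment history is left out of it. Mastectomy leaves no gland to measure on that side. Conserving surgery and radiotherapy leave a breast that can be measured and may be reported as free of suspicious findings.

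Such treatment may be one-sided. If it shifts T1 or T2, the treated woman's left-right difference reflects treatment as well as natural asymmetry, and her treated breast pulls the pooled baseline. The side comparison is the more exposed of the two, because the whole shift falls on one side of a within-woman difference, whereas in the baseline it is diluted over all breasts.

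**Working it through.** **The text.** Take a woman with one breast treated by conserving surgery or radiotherapy and follow her through the plan.
- Sections 3.1 and 3.2: eligible.
- Section 4.2.1: approached in sequence like anyone else.
- Section 4.2.4: her current MRI report is read for normal status. The term is undefined, and no consequence is given if it is not met.
- Section 1.5: a region is placed in parenchyma that the reader judges normal. This may avoid a visible scar, but there is no rule on irradiated tissue.
- Section 7.3: both breasts are analysed.

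No step removes the treated breast.

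**The plan's own figure.** Section 7.2 gives T1 power of 0.858 for a null ICC of 0.82, a true ICC of 0.72, 120 images (30 women × 2 breasts × 2 locations) and two measurements each. With Fisher z, z(r) = 0.5 × ln((1+r)/(1−r)), z(0.82) = 1.157 and z(0.72) = 0.908. Then (1.1568 − 0.9076) × √119 − 1.645 = 1.073, and Φ(1.073) = 0.858. It reproduces at one-sided 0.05, as do the other four stated powers. None of them concerns the left-right comparison.

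**Inputs for size (all assumed; none is in the documents).** Units are SDs of T1 or T2 in untreated breasts.
- f: share of women with one treated breast, 0.10 to 0.20.
- d: shift in the treated breast, 0 to 1 SD, with the side random.
- Natural SD of the left-right difference: 0.4, so variance 0.16.

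**How often.** The expected number among 30 is 30f, or 3 to 6. The chance of at least one is 1 − (1−f)^30 = 0.958 at 10% and 0.999 at 20%. Even at 5% it is 0.785.

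**Side comparison.** Variance of the difference = 0.16 + f·d². Efficiency loss = 1 − 0.16/(0.16 + f·d²).

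| Shift d | f = 0.10 | f = 0.20 |
|---|---|---|
| 0 | 0 | 0 |
| 0.25 | 1 − 0.16/0.16625 = 4% | 1 − 0.16/0.1725 = 7% |
| 0.5 | 1 − 0.16/0.185 = 14% | 1 − 0.16/0.21 = 24% |
| 1 | 1 − 0.16/0.26 = 38% | 1 − 0.16/0.36 = 56% |

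At d = 1 the SD of the difference rises from 0.40 to 0.51 (√0.26) or 0.60 (√0.36).

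**Baseline mean.** One breast in two is affected in a share f of women, so the mean moves by (f/2)·d. At d = 1 this is 0.05 to 0.10 SD; at d = 0.5 it is 0.025 to 0.05 SD.

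**The case against.** The strongest reply is that the harm depends on something the documents never state: that earlier treatment changes T1 or T2 in breast tissue still present at screening. That stands. If there is no shift, there is no loss.

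It is also fair that the plan shows intent. The synopsis, the region-of-interest wording, the report check and Section 7.2 all refer to normal subjects or tissue. These are real but partial safeguards. They rest on the current report and the reader's eye, and none mentions treatment. In a feasibility study of 30 women, recruiting ordinary screening patients is a legitimate choice, which is why the fix leaves eligibility alone.

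Three stronger readings do not hold:
- A reader might infer that the side comparison is shown to be confounded, or that half its sample is lost. The 38-56% figure belongs to a 1 SD shift only, and a larger natural left-right SD would shrink it. With treatment on random sides, the effect is extra spread rather than a systematic left-right bias.
- A reader might infer that the stated power fails. A stable offset is present in both repeat measurements and creates no disagreement between them. It can raise the ICC by adding variance between images (from 0.72 to about 0.733-0.743 at a 1 SD shift), but this rests on the same assumptions. Section 7.3 gives the side comparison no test or power that could be lost.
- A reader might infer that a published normal range would be wrong. The plan promises baseline values and a confidence interval for the ICC, not a reference interval.

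**Conclusion.** The point holds as a gap in the definition of the analysed tissue. Followed as written, the plan lets a breast with earlier conserving surgery or radiotherapy count as normal gland and enter a contrast named in the primary endpoint. This conclusion rests on the text alone.

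Its numerical importance is conditional. Under the assumed 10-20% share and left-right SD of 0.4, the effect on the side comparison runs from nothing (no shift) through modest (0.25-0.5 SD) to serious (1 SD). The effect on the baseline mean is small throughout. The point does not dispute the sample size. It is a cheap improvement worth making before analysis, not a flaw that invalidates the study.

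**What to change.** Keep eligibility as it is and make two changes.

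1. In Section 4.2.4, extend the abstraction from the MRI report to the relevant medical history, and record earlier breast-conserving surgery and breast/chest radiotherapy by side. The table in Section 4.3 already schedules record abstraction at one week and again after 30 cases.
2. In Section 7.3, add: *A breast with prior conserving surgery or radiotherapy is excluded from the normal-tissue baseline, and that woman from the left-right comparison; an all-breasts analysis is reported as sensitivity.*

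**Cost.** There is a little more abstraction work, because nothing says the MRI report records treatment by side. At the assumed shares, 3 to 6 breasts leave the baseline and 3 to 6 women (10-20%) leave the side comparison. On precision alone, exclusion pays only if 0.16/(0.16 + f·d²) < 1 − f, that is d > √(0.16/(1−f)), or about 0.42-0.45 SD. Below that, the reason for exclusion is that the comparison then describes untreated tissue, and the all-breasts analysis shows what it cost.

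The ICC analysis can keep all 120 images and its stated power. If it were also limited to untreated breasts, 6 to 12 images would go (two per breast). By the same formula, T1 power would be Φ(0.2492 × √113 − 1.645) = 0.842 at 114 images, or 0.824 at 108. Section 7.3 should say which set the ICC uses.

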4. STUDY PLAN

4.1. STUDY SCHEMA

4.2. Study Procedures

The patients will have a set of additional research scan of no more than 12 minutes scan time (MRF) within their primary screening breast MRI study. Patient will receive their standard clinical care as usual. No follow up needed for this observational study.

4.2.1. Enrollment/Recruitment

A total of 30 women will be enrolled to this study. The 30 study subjects will be consecutively recruited from women who are scheduled to undergo a screening MRI. Eligible patients will be identified by research staff review in coordination with the UNC Breast Clinic.

Once a patient has been referred, the patient will be approached by a coordinator from Radiology to assess interest in participation.

All eligible women who agree to participate in the study will be asked to come to their MRI appointment thirty minutes early to complete the informed consent process.

Review of the consent will take place in the privacy of an exam room, or when possible, a sample consent form will be sent to the patient via email prior to the patient's visit to allow for ample review.

4.2.2. Research Imaging

4.2.2.1. Imaging Procedures

The investigational MR protocol will be implemented on the existing MR scanners without any modifications to the existing, FDA approved machine,

equipment, or safety standards. Patients will receive their standard of care imaging. During the screening scan, they will receive the research sequence. The additional sequences will be performed at no cost to the patient other than a small increase in the amount of time spent inside the MR scanner. The additional sequences are 12 minutes in total and do not place individuals at any increased risk.

4.2.3. Standard of Care Biopsy

Almost all of the patients undergoing screening MRI do not have breast cancer. No further intervention with biopsy in this screening population. There is no change of standard of care for the screening population.

4.2.4. Medical Record Abstraction

The breast MRI report will be extracted one week after completion of the MRI exam for confirmation of normal status.

4.3. Time and Events Table

	Pre-study 30 minutes before MRI	Time Point 1 At MRI exam	Time Point 2 1 week After MRI exam	Time Point 3 After 30 cases completed MRI
Informed Consent	X			
Breast MRI with research MRF		X		
Medical Record Abstraction			X	X
Imaging analysis				X

*Include any necessary notes detailing specifics of procedures outlined in table.

5. INVESTIGATIONAL DEVICE

5.1. Investigational Device Description

Investigational sequences will be developed at UNC. The proposed study will be performed on the 1.5T MR scanners: (1) Main campus Siemens Avanto, Invivo 7-channel; (2) Out-patient Imaging center: Siemens Magnetom Aera, Sentinel Coil. The scanners are FDA approved and all new sequenced

possess the same safeguards as standard (FDA approved) clinical sequences to prevent harm to subjects. The study does not need any contrast administration unless it is required for standard clinical examination. For each consented subject, the additional scans will add no more than 12 minutes to the total scanning time. That is 6 minutes with two MRF sequences (3 minutes on each MRF sequence) pre-contrast enhancement phase and 6 minutes with two MRF sequences at the end of post contrast enhancement phase.

The investigational MR protocol will be implemented on the existing MR scanners without any modifications to the existing, FDA approved machine, equipment, or safety standards. Patients will receive their standard of care imaging. In addition, they will receive the research sequence. The additional sequences will be performed at no cost to the patient other than a small increase in the amount of time spent inside the MR scanner. The additional sequences are no more than 12 minutes and do not place individuals at any increased risk.

The research images will not be interpreted or analyzed for clinical decisions related to the patient. As such, this study will request that the IRB make a determination that this study is no greater than minimal risk. This study meets all the requirements for an NSR determination including:

- The device will not be implanted.
- The device is not intended to support or sustain human life.
- The device is not being used of substantial importance in diagnosing, curing, mitigating, or treating disease.
- The device does not present a potential for serious risk to health, safety, or welfare of a subject.

